The duration of the randomized study phase is from consent until two weeks after the second psilocybin session is approximately six weeks. All participants who received the full 25 mg dose of psilocybin and participants who received 4 mg psilocybin and declined to take part in the open-label session will, if able to do so, complete the two-month follow-up approximately three months (or 12 weeks) after consenting to take part in the study. From potential baseline to follow-up two weeks after the second psilocybin session, the open-label study phase lasts approximately one more month, so that subjects finish in 3.5 months (14 weeks). While it is exceedingly unlikely that participants who complete the open-label phase will take part in a follow-up two months after the second open-label psilocybin session, doing so would make the study last five months. On average, it is expected that participants will remain in the study for approximately three months, either completing the follow-up two months after the second experimental session or the follow-up two weeks after the second open-label session.

Method

The study will enroll nine people with stage IV melanoma diagnosed with anxiety or with HADS anxiety scores of 8 or higher. This study will use a randomized, active-placebo controlled, double-blind design to examine the effects of two day-long sessions of

psilocybin-assisted psychotherapy with either full (25 mg) or active placebo (4 mg) dose psilocybin, given along with non-drug preparatory and integrative psychotherapy sessions. Participants must have a primary caregiver who consents to be assessed as part of a related protocol examining caregiver anxiety. After participants and a selected caregiver give written consent, participants will undergo psychiatric screening and a selective drug screen to confirm study eligibility. If subjects are eligible, they and their caregiver will be administered baseline evaluations by an independent rater.

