Psychotherapy will be performed by one male and one female psychotherapist. The study consists of at least two introductory sessions with the investigator-psychotherapists, two experimental sessions scheduled within a seven to 14-day interval that include an overnight stay at the clinic, psychotherapy follow-ups 24 hours after each psilocybin-assisted session, a second interim and preparatory non-drug psychotherapy session scheduled between the first and second psilocybin sessions, and evaluation two weeks after the second experimental session. Due to the short life expectancy of subjects in this study, subjects will be considered to have completed the study if they complete the outcome measures scheduled 2 weeks after the second experimental session.

Participants in the active placebo condition are eligible for an open-label study continuation. Participants will be re-screened no later than a week after the blind is broken to make sure they still meet study criteria. If they are ineligible, or choose not to enroll in the open-label study, they will be scheduled for another follow-up assessment two months after the second psilocybin-assisted session. If they are eligible and choose to enroll in the open-label continuation, they may do so, undergoing psilocybin-assisted sessions occurring within another seven to 14 day period. Participants in the full experimental dose condition are ineligible for the open label study phase.

The open-label phase of the study will follow nearly identical procedures to those used in the randomized phase. Participants will be re-assessed on all study measures two weeks after their second psilocybin session and again at two months, should participant health permit it. Subjects need not complete any portion of the open-label phase or the two-month follow up phase for their participation in the study to be considered completed.

Time and Events

Time and Events P-CA1	Baseline and Screening			Therapy and Evaluation 1					Therapy and Evaluation 2		
	V1	V2	V3	V4	V4.5	V5	V6	V7	V8	V9	V10
Visit #	V1	V2	V3	V4	V4.5	V5	V6	V7	V8	V9	V10
Type of Visit	Screening	IC Review	Psychiatric Eval	Intro Psychotherapy	Intro psychotherapy2	Psilocybin Session1	Therapy follow-up	Non-drug psychotherapy	Psilocybin Session 2	Therapy follow-up	2 wk follow-up
Approximate Study Day			0	7	10	14	15	21	29	30	43

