Participants must be able to complete self-report measures and understand and answer items in clinician-administered measures. The investigators will perform the MMSE to assess mental status and review medical records for indicators of subsequent metastasis or other CNS disease since the end of the randomized or open-label phase. Only participants with MMSE scores of 27 or higher and without any signs of serious CNS disease will undergo assessments at this time. Participants will complete the HADS, STAI, FACIT-Sp, EORTC-QLQ-C15 and SELF, and the investigators will administer the HAM-A and HAM-D and a pain level measurement for the day of the two-month follow-up. The investigator will assess participants for symptoms of HPPD by asking about cardinal symptoms of perceptual disturbances and distress at their occurrence.

Visit by Visit Description

Participants who consent to take part in the study will undergo the following sequence of events:

The randomized, blinded study phase:

- **Psychiatric Evaluation and Baseline (Visit 3):** A two-hour long psychiatric evaluation. The principal investigator will diagnose psychiatric disorders via SCID. Mental status will be assessed with MMSE. Participants will also complete measures of anxiety (HADS anxiety, STAI), depression (HADS depression), spirituality (FACIT-SP) and quality of life (EORTC-QLQ-C15). The investigators will also administer observer-scored measures of anxiety (HAM-A), depression (HAM-D), and ability to perform everyday life functions (KPRS). If a participant meets study eligibility criteria after psychiatric evaluation, he or she will be scheduled for an introductory psychotherapy session.

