psychotherapy. Participants will complete a measure of their feelings and experience as a research participant (RRPQ).

Two-month follow-up

- **Two Month Follow Up Visit(s):** A 90 to 120 minute long follow up occurring two months after the second experimental psilocybin-assisted session for all full (experimental) dose participants and any active-placebo participants who did not take part in the open-label study phase, and two months after the second open-label psilocybin-assisted psychotherapy session for active placebo participants who enrolled in the open-label study phase. Only participants who are willing and able to complete study measures will take part in the two-month follow-up. Participants will complete all the measures of anxiety, depression, spirituality and quality of life described above. In addition, they will complete the daily pain and medication diaries for the day of the two-month follow-up, and the investigators will assess them for HPPD occurrence. There are no more visits for any participants after completing the two-month follow-up. Participants may briefly meet with the investigators, but they will not undergo any further psychotherapy.

Removal of Subjects from Therapy or Assessment

The participant, or where applicable, the participant's legally acceptable representative(s) can withdraw consent for participation in the study at any time without prejudice. The investigator can withdraw a subject if, in his or her clinical judgment, it is in the best interest of the subject or if the subject cannot comply with the protocol.

The subject will be clinically monitored after withdrawal, the cause of which will be recorded on the "Study Termination" CRF and, where appropriate, on the subject's medical records. Where the withdrawal of a subject resulted from an adverse event, this will be documented in accordance with the procedures in section.

Whenever possible, the tests and evaluations listed for the termination and outcome visits will be carried out.

Premature Discontinuation of the Study

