Is an important and significant medical event that may not be immediately life threatening or resulting in death or hospitalization but, based upon appropriate medical judgment, may jeopardize the patient/subject or may require intervention to prevent one of the other outcomes listed above.

Adverse events which do not fall into these categories are defined as **non-serious**. It should be noted that a severe adverse event need not be serious in nature and that a serious adverse event need not, by definition, be severe.

In addition, a pre-existing event or condition that results in hospitalization should be recorded on the medical history. The hospitalization would not result in the event or condition being reported as an on study SAE unless, in the view of the investigator, hospitalization was prolonged as a result of participation in the clinical trial or was necessary due to a worsening of the pre-existing condition. This is because the onset of the event (the reason for the procedure) occurred before the subject was entered in the trial. Hospitalization for cosmetics, non-emergency prophylaxis or abortion does not result in an SAE report unless, in the view of the investigator, hospitalization for these procedures was prolonged as a result of participation in the clinical trial.

Adverse Event Collection

All serious adverse events will be collected for the duration of the study. All SAEs which occur during the course of the trial, whether considered to be associated with the study IP or not, have to be reported **within 24 hours** or at the latest on the following working day by telephone or fax to either of the following:

Medical Monitor: [name] [contact] [contact]

Study Monitor: [name] [contact]; [name]

Adverse events that will be collected for the duration of the study are:

Pain using the VAPS.

Events requiring a physician visit or an intervention, not related to planned treatments for baseline conditions.

Any adverse event leading to withdrawal from the study.

Additional adverse events collected for seven days after each experimental session are:

Common side effects.

Exacerbation of anxiety.

Collection of Concomitant Medications

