Earlier studies found changes in personality or neuropsychological function after frequent chronic LSD use. However, a review of these studies concluded that they all shared a number of methodological flaws (Halpern and Pope 1999) that included retrospective study design, failure to account for effects of other drugs, possible pre-existing morbidity, and the association of LSD with subcultures that valued specific personality types. In their review and analysis, Halpern and Pope concluded that long-term changes in personality or psychological function, if they existed at all, were liable to be subtle or not clinically significant (Halpern and Pope 1999). It is notable that two months after psilocybin administration, investigation in psilocybin-naïve individuals, investigators found that friends or relatives of the study participants stated that after participants received psilocybin, they underwent positive changes in their attitudes and behavior (Griffiths et al. 2006).

Some people who have used serotonergic psychedelics, such as LSD or psilocybin, experience persistent and distressing alterations in mostly visual perception that last from weeks to years after use. This condition is now diagnosed as hallucinogen persistent perception disorder (HPPD), and is not referred to by the term “flashbacks,” which better

describes an experience more akin to traumatic recall of an intensely upsetting experience, as a “bad trip.” By contrast, HPPD involves changes in visual perception rather than a re-experiencing of feelings or memories first experienced while under the influence of a psychedelic. There is a paucity of data concerning the prevalence of HPPD due to psilocybin use.

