
Are positive results due to participant's medications? Yes No N/A

Does subject continue to **meet all inclusion and no exclusion criteria**? Yes No

If no, specify: _____

Visit 5 - Experimental Session # 1: Administration

Record time of initial IP administration ____:____ AM / PM

Record Bottle number of Investigational Product _____

Visit 5 - Physiological measures and Body temperature:

Please record maximum and average figures for each measure, and time of measurement for maximum increase. Body temperature should be recorded in degrees Centigrade.

	Average baseline	Maximum Change in Value	Time Max Change Recorded	Post-Drug average
Systolic Blood Pressure (mm/HG)				
Diastolic Blood Pressure (mm/Hg)				
Pulse (BPM)				

Was blood pressure ever above 160/110? Yes No

If "Yes," for how long was blood pressure higher than 160/110? _____ h _____ min.

If the duration of elevated blood pressure was less than 1 hour, write time in minutes only and write "0" (zero) in "hours."

Visits 5-6 Spontaneously Reported Side-Effects:

Please record the maximum intensity of any spontaneously reported effects up to 24 hours after drug administration.

Visit	Visit 5 Experimental Session #1		Visit 6 24 hrs post
	Duration in hours	Intensity	Intensity
Report Max Intensity for the 24 hour period 0= None Reported 1= Mild 2= Moderate 3= Severe	Report Duration to the nearest hour for the first 24 hours only		
Check None if no symptoms are reported for the 1 st 24 hours		 None	 None
Anxiety			
Chills/feeling cold			
Derealization			
Depersonalization			
Difficulty Concentrating			
Dilated pupils			
Emotional Lability			
Feeling hot			
Impaired cognition			
Impaired gait/balance			
Nausea			
Objects/people different			
Parasthesias			
Perspiration			
Simple visual images			
Somatization			
Repetitive thoughts			
Time perception altered			
Unusual thoughts			
Visual illusions			
Weakness			
Other:			

Visit 6 States of Consciousness Questionnaire

Visit 6 (24 hours post-psilocybin session 1)

Please write in the score or scores for each outcome measure. All scale scores must be complete

Scale	Visit 4	Visit 4.5	Visit 5	Visit 6
SCQ				
Internal unity				
External Unity				
Transcendence of Time and Space				
Ineffability and Paradoxicality				
Sense of Sacredness				
Noetic Quality				
deeply Felt Positive Mood				
Total				
SELF				
Personal				
Middle				
Transpersonal				
Total				

NK cell Count

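### HPPD is asked about after dosing only at the optional two-month follow-up, so a case that leads to no medical care can go unrecorded in a participant who does not reach that visit

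*Protocol*

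**What the plan says.** **Where HPPD is asked.** The assessment text of the Two-Month Follow-up section states: "The investigator will assess participants for symptoms of HPPD by asking about cardinal symptoms of perceptual disturbances and distress at their occurrence". The Visit by Visit Description repeats this for the same visit: "the investigators will assess them for HPPD occurrence". In Time and Events, the HPPD row stands only in the two-month table, in the F/U Screening column. The table for Visits 1 to 10 has no such row.

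**Who reaches that visit.** Under Method: "Subjects need not complete any portion of the open-label phase or the two-month follow up phase" for their participation to count as completed. Under Visit by Visit Description: "Only participants who are willing and able to complete study measures will take part in the two-month follow-up". The two-month assessment text further limits assessments to those with an MMSE score of at least 27 and no sign of serious CNS disease. Sample Population and Subjects says losses before this visit are not replaced. Planned Duration of the Study says "it is exceedingly unlikely that participants who complete the open-label phase will take part in a follow-up two months after" their second open-label session. The same section expects full-dose participants, and placebo participants who decline open label, to attend if they are able.

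**What else would catch it.** Adverse Event Collection keeps four things for the whole study: serious events, pain scores, events needing a physician visit or intervention, and events leading to withdrawal. It then adds: "Additional adverse events collected for seven days after each experimental session are" common side effects and exacerbation of anxiety. Time and Events nevertheless marks Common Side Effects at Visit 10.

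**Why HPPD is of interest.** The section on chronic neuropsychological effects says some users "experience persistent and distressing alterations in mostly visual perception that last from weeks to years after use".

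**The concern.** The protocol decided that HPPD deserves its own question, then placed that question only at a visit that is optional and depends on the participant's health. Visit 10 defines completion, so every counted completer attends it, and it is the last blinded contact. By two months everyone has been unblinded, and placebo participants who entered open label have also received 25 mg. No post-dose answer to the HPPD question is therefore ever obtained under the blind.

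The participants least likely to be asked are the open-label completers, who by then have had four psilocybin sessions. If one of them, or a full-dose participant who becomes too ill to return, has visual disturbance that leads to no physician visit, intervention or withdrawal, nothing in the collection rules requires it to be recorded. A later statement that no HPPD occurred would describe only those well enough to attend.

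**Working it through.** The protocol states no figure for HPPD ascertainment, so there is none to reproduce. The check sets the passages side by side and adds some simple arithmetic.

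1. **Post-dose visits with an HPPD question.** Visits 5 to 10: none, in either the table or the text. Open-label visits through Visit 18: none in the text. The material at hand shows no schedule table for those visits, so only the prose could be checked. Two-month follow-up: one.

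2. **Is Visit 10 late enough to be informative?** Time and Events puts session 1 at day 14, session 2 at day 29 and Visit 10 at day 43. That is 43 − 14 = 29 days after session 1 and 43 − 29 = 14 days after session 2. Both fall in the range of weeks that the protocol gives for HPPD.

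3. **The seven-day window.** Visit 10 is 14 days after session 2, outside the window in Adverse Event Collection, yet the schedule marks Common Side Effects there. The two passages do not agree on what is collected.

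4. **How many are asked.** Allocation is six to 25 mg and three to 4 mg. If all three placebo participants complete open label and, as the protocol expects, do not return, at most 9 − 3 = 6 are asked. With the question at Visit 10, all nine completers are asked.

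5. **Loss by death alone (illustration).** Assume exponential survival from Visit 10 with a median m of 3 to 12 months: S(t) = exp(−ln 2 × t / (30.44 × m)), t in days.
   - To day 89, t = 89 − 43 = 46: S = 0.705 at m = 3, 0.890 at m = 9, 0.916 at m = 12. Of six full-dose participants, 4.2 to 5.5 are expected alive.
   - To day 132, t = 132 − 43 = 89: S = 0.509 at m = 3, 0.798 at m = 9, 0.845 at m = 12. Of three open-label participants, 1.5 to 2.5 are expected alive.

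   Illness, refusal and the MMSE/CNS check add losses that the protocol does not quantify.

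6. **What zero cases would mean.** The one-sided 95% upper limit is 1 − 0.05^(1/n). For n = 9 it is 28.3%. For n = 6 it is 39.3%. The nine include three who have had only 4 mg by Visit 10, so 39.3% is the relevant figure for the full dose.

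7. **Chance of any case at the quoted ceiling.** The risk section reports a survey rate of at most 1%. At 1%, 1 − 0.99^9 = 8.6% among nine and 1 − 0.99^6 = 5.9% among six.

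8. **Who is gated.** The schedule puts the HPPD question at F/U Screening, before the main visit. The assessment text lists it after the sentence restricting assessments to those who pass the MMSE/CNS check. Whether someone who fails the check is still asked cannot be determined.

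**The case against.** The best defence has four parts.

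- **Timing.** Two months separates a persisting disorder from a passing after-effect better than two weeks does. This stands, and is why the two-month question should stay. It does not justify having no earlier question for people not expected to return.
- **Other routes.** A case that leads to care or withdrawal is recorded whenever it occurs. Data Analysis says spontaneously reported and observed side effects are recorded. Participants meet the investigators at Visit 10, where the schedule marks Common Side Effects. On withdrawal, the termination and outcome evaluations are to be done where possible. These routes narrow the gap, but none requires the HPPD question to be put to everyone.
- **Attendance.** A reader might infer that the protocol expects many participants to miss the visit. It does not. Its explicit doubt covers at most three of nine, it expects the others to attend if able, and the survival illustration keeps most full-dose participants alive to day 89.
- **Importance.** A reader might also take HPPD to be the only delayed harm named. The protocol also names prolonged psychotic states and discusses lasting personality or neuropsychological change. The primary objective defines safety as recorded adverse and serious adverse events, without naming HPPD. HPPD is singled out only in having its own scheduled question.

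Two further inferences fail. The draft form that says "Please record the maximum intensity of any spontaneously reported effects up to 24 hours after drug administration" is a sample for Visits 5 and 6, so it does not show what would be recorded at Visit 10. The threshold of four participants in Data Analysis triggers the two-month analyses of the anxiety, depression, quality-of-life and spirituality scores; it is not a planned HPPD denominator.

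**Conclusion.** The gap is real and limited. The only post-dose HPPD question sits at an optional visit that up to three of nine participants are not expected to reach and the others reach only if able. A case outside the seven-day window that leads to no care can go unrecorded in anyone who misses it. Visit schedules and collection windows are protocol content, so this is not something a statistical analysis plan would settle.

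The consequence is incomplete ascertainment. It is not a biased rate of known size, and the rate could not be estimated usefully in any case: with no cases the upper limit is 28% from nine and 39% from six, and at a 1% rate even one case among nine is unlikely. For Visit 18 the conclusion rests on the visit description alone. It also assumes that an unasked participant may not volunteer the symptom. The change is worth making because it is cheap and lets a negative statement cover every completer.

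**What to change.** 1. Put the existing two-month HPPD question to every participant at Visit 10, before unblinding, and at Visit 18 for open-label participants. Keep it at two months as the check on persistence.
2. Reconcile the Common Side Effects mark at Visit 10 with the seven-day window in Adverse Event Collection, so that perceptual disturbance is recorded through Visits 10 and 18. Recording of anxiety exacerbation need not be extended for this purpose.
3. State whether participants who fail the MMSE/CNS check at follow-up screening are still asked, and make the schedule and the assessment text agree.
4. Report HPPD by dose received, with the number actually asked as the denominator.

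The cost is a few questions at visits already scheduled, new entries in the schedule and a line on the case report form. The one drawback is that some positive answers at two weeks will be transient. The two-month question resolves these for those who attend; for the rest they should be reported as unconfirmed.
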